#### 5.5 Subgroup Analysis

Subgroup analysis will include those patients for whom measurements are available.

The first objective of subgroup analysis is within the whole dataset, to account for potential variation in the treatment effects between

patients with paroxysmal and non-paroxysmal AF: Paroxysmal AF vs. Persistent Chronic or longstanding AF.

individual centres (as a random effect to allow for heterogeneities in small centres

different cardiac surgical procedures

different surgeons.

different lesion sets.

The different lesion sets are to be defined as follows:

minimal LA lesion set: pulmonary vein isolation only ± LA appendage line

more extensive LA lesion set excluding mitral annulus

more extensive LA only lesion set including mitral annulus

minimal LA lesion set + RA lesion set

more extensive LA lesion set excluding mitral annulus + RA lesion set

more extensive LA lesion set including mitral annulus + RA lesion set

In the event that patients are too sparsely-distributed across the 6 categories, the categories will be combined into 4, by combining (i) with (ii) and combining (iv) with (v). If this is still too sparse to facilitate comparison, then the lesion set subgroup will be reduced to a comparison of category (vi) to all other groups.

For the Quality-Adjusted Survival Endpoint, a linear regression model will be fitted to the Area Under the Utility Curve, with baseline EQ5D score, surgeon, surgical procedure, treatment group, subgroup variable and the subgroup-by-treatment interaction variable. The treatment modifying effect will be reported with a 95% confidence interval. The Area under the utility curve will be appropriately transformed prior to performing subgroup analyses, and the results back-transformed where necessary.

For the Return to SR Endpoint, a logistic regression model will be fitted to heart rhythm at 12 months with the baseline heart rhythm, surgeon, surgical procedure, treatment group, subgroup variable of interest and its interaction term with treatment group. The odds ratio of the interaction term between treatment and subgroup variable will be reported with 95% confidence interval and p-value for the data seen, under the null hypothesis that there is no difference in the treatment effects on patients within different subgroup of interest.

The second objective is within the Routine+Maze treatment group, to account for variation in the treatment effects between

different ablation devices

completeness of lesion sets – both on a continuous scale and categorised as 0-4, 5-9, 10+.

In each subgroup analysis listed above, the regression model will include only patients in the Routine+Maze treatment group. The interaction effect will then be tested in the same manner as for the previous interaction effects. The odds ratio or parameter estimate of the subgroup variable will be reported with 95% confidence interval and p-value for the data seen, under the null hypothesis that in the Routine+Maze treatment group, there is no difference in the treatment effects on patients within different subgroup of interest.

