## 1.2 Study design

The Amaze trial is a pragmatic, multicentre, prospective, double blind, randomised controlled trial to compare clinical, patient-based and cost outcomes for patients with pre-existing AF who undergo routine cardiac surgery either with or without an adjunct device-based ablation procedure.

The trial is double blind to the extent that neither the patient nor the cardiologist who analyses the 4 day ECG, nor the quality of life assessor should be aware which group the patient has been allocated to.

Eligible patients are randomised (in a 1:1 ratio) to receive either their routine cardiac surgery with no additional procedure or their routine cardiac surgery with an additional device-based AF ablation procedure.

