### 4.3 Data collection during and after surgery

Data collection is based on the recommendations of Shemin et al.[13] and includes procedural details-including the lesion set in the experimental group. Data collected after surgery includes: mortality, stroke/thromboembolic events, medications, EuroQoL, health-related quality of life, cardioversion plan if appropriate, 4-day ECG recordings, resource use, adverse events.

Data are collected during surgery, at discharge, 6 weeks after surgery (at a routine service visit), at 6, 12 and 24 months after surgery during out-patient research visits and annually thereafter by telephone follow-up.

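### SAP 5.5: the lesion-set-by-treatment interaction cannot be estimated because only the maze arm has lesion sets, and the maze-only analyses state a null hypothesis that their reported coefficient does not test

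*SAP*

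**What the plan says.** Section 5.5 of the SAP has two subgroup objectives.

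The first begins "The first objective of subgroup analysis is within the whole dataset, to account for potential variation in the treatment effects between" and lists AF type, centre, surgical procedure, surgeon and "different lesion sets". Lesion set has six categories and a rule for thin data: "In the event that patients are too sparsely-distributed across the 6 categories, the categories will be combined into 4", and if that is still too sparse, "then the lesion set subgroup will be reduced to a comparison of category (vi) to all other groups". For each primary endpoint the model contains treatment group, the subgroup variable and their product, along with surgeon, surgical procedure and the baseline value. No exception is made for lesion set.

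Section 1.2 says that controls receive "their routine cardiac surgery with no additional procedure". Section 4.3 includes, among the data collected, "procedural details-including the lesion set in the experimental group".

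The second objective concerns ablation device and completeness of the lesion set, and the regression is restricted to Routine+Maze patients. It continues: "The interaction effect will then be tested in the same manner as for the previous interaction effects". The sentence after that names the reported quantity, which is the coefficient of the subgroup variable with its confidence interval and p-value. The null attached to it is that treatment effects do not differ between subgroups of the maze arm.

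**The concern.** A treatment interaction asks whether the maze-versus-control difference changes across levels of a factor. That needs patients from both arms at more than one level. Lesion set has no control patients at any of its six levels, so the question cannot be put to these data. In the maze-only models the treatment variable is constant, so there is no interaction there either. The text announces an interaction test, reports a main effect, and states a null about a third quantity.

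Section 5.2 makes this more than loose wording. It tells the analyst to enter every specified variable and report the significance of each. The plan does not say what to do when a specified term has no degrees of freedom, so the re-specification would be made after the data are seen. An association between technique and outcome could then be reported as if it were a difference in treatment effect between lesion sets or devices.

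**Working it through.** The SAP gives no figure for these analyses, so there is none to reproduce. The check is the rank of the design matrices that Section 5.5 describes.

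**Inputs.** 200 patients per arm (Section 1.4.1); lesion set filled in the maze arm only (Sections 1.2 and 4.3); K = 6, 4 or 2 categories (the thin-data rule in Section 5.5). Other covariates are left out, since adding them cannot restore the missing information.

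**1. Whole dataset, controls coded as having no lesion set.** Let T be treatment and L_k the indicator of category k. The columns are the intercept, T, L_1 to L_K, and L_1·T to L_K·T, which makes 2 + 2K. Because L_k = 1 only when T = 1:

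- L_k·T = L_k for every k, so each interaction column duplicates a main-effect column;
- L_1 + … + L_K = T, so T is not separately identified either.

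The rank is therefore K + 1, one for each occupied cell (controls plus K lesion sets).

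**2. Whole dataset, only patients with a recorded lesion set.** Section 5.5 limits subgroup analyses to patients with available measurements. Read that way, all controls drop out and T is constant. With one category as reference there are 2K columns and the rank is K.

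| Categories | Controls coded none: rank of columns | Degrees of freedom added by interaction | Recorded lesion set only: rank of columns |
|---|---|---|---|
| 6 | 7 of 14 | 0 | 6 of 12 |
| 4 | 5 of 10 | 0 | 4 of 8 |
| 2 | 3 of 6 | 0 | 2 of 4 |

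**3. The last fallback, with controls counted among the other groups.** The SAP does not say whether they are. Let V = 1 for category (vi) and 0 for everyone else, controls included. V = 1 still implies T = 1, so V·T = V and only 3 of the 4 columns (intercept, T, V, V·T) are distinct. The interaction remains unidentified.

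**4. Maze arm only, completeness on the continuous scale.** With a treatment interaction, the columns are the intercept, T = 1, C and C·T = C, giving rank 2 of 4. Without T and the interaction the rank is 2 of 2. The same holds for lesion set in the maze arm without treatment terms: 6 of 6, 4 of 4 and 2 of 2 columns. The subgroup coefficient is therefore estimable and the interaction is not.

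**5. Comparison.** Paroxysmal versus non-paroxysmal AF is defined in both arms. Its model with interaction has rank 4 of 4, so the general form in Section 5.5 works for that kind of factor.

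**The case against.** The strongest reply is that the maze-only analyses are sound in substance. Section 5.5 names the subgroup coefficient as the reported quantity, and that coefficient is estimable. A reader might infer that nothing under either objective can be estimated. The SAP does not support that: what fails is the interaction in both places and the null in the second.

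It can also be said that the models already adjust for surgeon and surgical procedure, and for baseline rhythm or baseline EQ5D, and that testing in the same manner carries these covariates into the maze-only models. This stands. Of the obvious prognostic factors, only AF type is absent.

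A reader might further infer that surgeons choose the technique, or that the software will print a misleading interaction odds ratio. The SAP shows neither. It does not say how lesion set or device is decided; it shows only that the randomisation in Section 1.5 does not allocate them. With 0 degrees of freedom, the interaction may simply fail visibly.

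Finally, the whole dataset is not useless for lesion set. Rank 7 means that seven group means are identified, so each lesion set can be compared with controls or with another lesion set if it is nested in the maze arm. That is correct and gives a second valid repair. It does not rescue the interaction as specified, and the contrasts remain non-randomised with respect to lesion set.

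**Conclusion.** Section 5.5 is wrong as written on two counts. The lesion-set-by-treatment interaction cannot be estimated with six, four or two categories, and the collapsing rule cannot help because it addresses thin cells, not an empty control arm. For device and completeness, the test named, the quantity reported and the null stated do not agree; the reported coefficient is a non-randomised association with outcome inside one arm.

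This rests on one assumption: that no lesion set, planned or actual, is recorded for controls. The SAP mentions it only for the experimental group. Controls who crossed over to ablation could make some terms computable, but only from a small, self-selected set of patients.

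The reach is limited. Both primary analyses, the key secondary analysis and the interactions for AF type, procedure, surgeon and centre are untouched, and the sample size has no bearing on the point.

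**What to change.** Amend Section 5.5 as follows.

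- Remove lesion set from the whole-dataset interaction tests. Keep those tests for AF type, procedure, surgeon and centre.
- Analyse lesion set in one of two ways, chosen in advance: within the maze arm, as for device and completeness; or in the whole dataset, nested in the maze arm with controls as a common reference. In the nested version, the test of interest is equality of the lesion-set coefficients.
- Check for aliasing with surgeon before choosing. If each surgeon mostly uses one lesion set, a maze-only model adjusted for surgeon has little left to estimate, whereas the nested version keeps each surgeon's own controls.
- Keep the planned covariates (surgeon, surgical procedure, baseline rhythm or baseline EQ5D) and add AF type, which Section 4.2 already collects at baseline.
- For lesion set, device and completeness, delete the treatment-interaction wording and state the null as no association between the technique variable and outcome within the maze arm.
- Say in the last fallback whether controls belong to the comparison group.
- Label these results exploratory and non-randomised. Section 5.8 already does much of this when it describes an exploratory look at the relation between completeness and organised atrial arrhythmia or junctional rhythm.

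The cost is SAP wording only. No new data and no change in sample size are needed.

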## 5.6 Key Secondary Endpoint Analysis

The key secondary endpoint, the rate to return stable SR at 24 months will be analysed in a similar way to the rate of return to SR at 12 month, but will include only those patients for whose measurements are available. The rate in SR at 24 months for Routine treatment group will be compared to that for Routine+Maze treatment group using a binary logistic regression model including baseline heart rhythm, surgeon, surgical procedure and treatment group. The odds ratio for the rate of return to SR at 24 months of Routine treatment group relative to the Routine+Maze group will be reported with 95% confidence interval and p-value for the data seen, under the null hypothesis that the rates of return to SR at 24 months are no different between the pairs of groups.

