### 2.3 Missing data

Data management will focus on the consenting process, participant eligibility, safety, data consistency and test outcomes. Attempts will be made to retrieve missing data on these areas via a thorough data cleaning process.

The levels of missing data and reasons for missingness will be investigated for the consenting process, participant eligibility, safety, data consistency and test outcomes. The quantity of missing data will be monitored by treatment group, and a summary of the number of patients with missing primary endpoint data and the quantity of missing data by treatment group will be reported.

For the intermediate primary endpoint (return to sinus rhythm at 12 months), if a patient withdraws consent or is lost to follow-up for further participation within 12 months, multiple imputation used to impute missing outcome (AF or SR at 12 months) as a function of the baseline heart rhythm, surgeon, surgical procedure and treatment group. Rubin's rules will be used to combine imputed datasets. If more than 5% of patients are withdrawn or lost to follow-up before 12 months, then the outcome will be imputed under the alternative patterns as sensitivity analyses. (See section 5.4.1)

For the final primary endpoint (Quality-Adjusted Survival at 2 years), where a patient is deceased before the end of follow-up, the utility value of 0 will be imputed for all

subsequent assessments. If the response is missing, and the patient is not known to be deceased, the missing value will be imputed using the method of multiple imputation. A “Last Observation Carried Forward” approach will be used as an alternative imputation technique for imputing other (non-death) missing values in a sensitivity analysis.

The primary analysis model will only require the baseline rhythm, surgeon and surgical procedure which are immediately recorded when patients attend the preadmission clinic and has consented to participate or during the period of surgery, so there is little concerns about missing data arising in this model. If any missing values in the covariates are reported, they will be imputed using a function of the known covariates and primary outcomes of interest.

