## 3 Population

### 3.1 Intention-to-treat Analysis

An intention-to-treat analysis will be the primary method for analysing and summarising the trial data. The intention-to-treat population is defined as all randomised patients, regardless of eligibility, withdrawal, compliance with the protocol, loss to follow-up or actual treatment received. Only patients who have withdrawn their consent for their data to be used in the study, or for whom written informed consent has not been received, will be excluded in this population. These patients will be analysed and summarised according to the intervention they were randomised to receive.

If more than 5% tests or trial conduct constitute a major protocol violation such as cross-over to the other arm or cancelling surgeries, the Complier Average Casual Effect analysis will be considered.

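### The 24-month sinus rhythm analysis (SAP 5.6) uses available cases only and ignores the recorded 12-month rhythm, so its odds ratio is open to bias if rhythm-related loss differs between arms

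*SAP*

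**What the plan says.** Section 5.6 states that SR at 24 months is analysed in a similar way to SR at 12 months, "but will include only those patients for whose measurements are available". The analysis is a "binary logistic regression model including baseline heart rhythm, surgeon, surgical procedure and treatment group", reported as an odds ratio with a 95% confidence interval and p-value. SR at 24 months is the first secondary objective in section 1.3.3.

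For the 12-month rhythm the SAP does more. Section 2.3 imputes missing values from baseline rhythm, surgeon, surgical procedure and treatment group, and adds: "Rubin's rules will be used to combine imputed datasets". Two sensitivity analyses in section 5.4.1 have a trigger: "If more than 5% of patients are withdrawn or lost to follow-up before 12 months". Sections 2.3, 5.4.1 and 5.6 give no counterpart for the 24-month rhythm.

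Section 4.3 lists 4-day ECG recordings among the data collected after surgery, with data collection "at 6, 12 and 24 months after surgery during out-patient research visits". The 12-month recording supplies a primary outcome (section 2.1).

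**The concern.** An available-case logistic regression is safe when loss depends only on the variables in the model. Rhythm after surgery is not one of them. It is a strong predictor of rhythm at 24 months, and it may plausibly affect whether a patient keeps attending. A patient seen at 12 months and lost before 24 months has contributed a 4-day recording that section 5.6 leaves unused.

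The 24-month comparison is the trial's evidence on whether the rhythm effect lasts. If patients back in AF leave follow-up more readily in one arm than in the other, that arm's SR rate among those measured is too high and the treatment odds ratio shifts with it. The SAP plans no analysis that would show this.

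**Working it through.** **The plan's own figure.** The SAP states no figure for 24 months. The nearest is section 1.4.1: 45% against 30% at 12 months, 80% power, two-sided 5%, 176 per group.

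- Without continuity correction: n = [1.960·√(2·0.375·0.625) + 0.842·√(0.45·0.55 + 0.30·0.70)]² / 0.15² = 162.3, so 163.
- With correction: n′ = (n/4)·[1 + √(1 + 4/(0.15·n))]² = 175.4, so 176.

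The stated figure is reproduced, and the 45% and 30% are used below.

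**Inputs.** From the SAP: 12-month SR p = 0.45 (maze) and 0.30 (control). Assumed, because the SAP gives nothing: P(SR at 24 | SR at 12) = 0.85, P(SR at 24 | AF at 12) = 0.10, and the loss rates in the table. Every patient is first taken to have a 12-month recording.

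**Truth.** SR at 24 months = 0.85p + 0.10(1 − p).
- Maze: 0.85·0.45 + 0.10·0.55 = 0.4375
- Control: 0.85·0.30 + 0.10·0.70 = 0.325
- Difference 0.1125 (11.2 points); odds ratio (0.4375/0.5625)/(0.325/0.675) = 1.62

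Odds ratios here are maze against control and unadjusted. The SAP reports the inverse, from the adjusted model.

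**Available-case estimate.** With m_S and m_A the loss rates in patients in SR and AF at 12 months, the rate in those measured is

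[0.85·p(1 − m_S) + 0.10·(1 − p)(1 − m_A)] / [p(1 − m_S) + (1 − p)(1 − m_A)].

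Example, maze with m_S = 8% and m_A = 22%: (0.85·0.414 + 0.10·0.429)/(0.414 + 0.429) = 0.3948/0.843 = 0.468. Against 0.325 in controls, the difference is 0.143.

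| Loss in maze (SR/AF) | Loss in control (SR/AF) | Difference | Odds ratio |
|---|---|---|---|
| 12% / 12% | 12% / 12% | 0.112 | 1.62 |
| 5% / 18% | 5% / 18% | 0.116 | 1.62 |
| 8% / 22% | 15% / 15% | 0.143 | 1.83 |
| 15% / 15% | 5% / 20% | 0.085 | 1.43 |
| 5% / 18% | 12% / 12% | 0.140 | 1.80 |
| 5% / 30% | 15% / 15% | 0.170 | 2.03 |

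The first two rows show no bias in the odds ratio. The next two give the quoted range: +3.0 points (about 0.6 of a standard error of 5.2 points) and −2.8 points. The last row is a stress case.

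**Effect on the test.** In simulation (200 per arm, 20,000 runs) with 12-month SR of 30% in both arms, the available-case test rejected in 7.6% of runs under the fifth row's losses and 16.0% under the last row's, against a nominal 5%.

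**What the 12-month rhythm recovers.** Standardising over 12-month rhythm within arm, the large-number limit of imputing from it, returns 11.2 to 11.3 points in rows three and four. That recovery is built into the set-up: loss depends only on 12-month rhythm, and everyone has that recording. Under equal random loss of about 15% there is no bias to correct, and the standard error falls only from 5.2 to 5.0 points.

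**If half of those lost have no 12-month recording.** In the fifth row, the maze patients still seen at 12 months are 0.45·(1 − 0.025) = 0.43875 in SR and 0.55·(1 − 0.09) = 0.5005 in AF. Their 24-month rate is (0.85·0.43875 + 0.10·0.5005)/0.93925 = 0.450, and the difference is 0.125. About half of the bias (0.140 − 0.112) remains.

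**The case against.** **Section 3.1 is not contradicted.** A reader might infer a conflict, since that section says "An intention-to-treat analysis will be the primary method for analysing and summarising the trial data" and defines the population as "all randomised patients, regardless of eligibility, withdrawal, compliance with the protocol, loss to follow-up or actual treatment received". But it settles who belongs and in which arm they are analysed. It sets no rule for missing outcomes. Section 2.3 limits outcome imputation to the two primary endpoints, and section 5.6 states its different rule openly. This objection stands.

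**The 12-month imputation adds little protection.** A reader might also infer that the 12- and 24-month results rest on different populations, so that a change between them is confounded. But section 2.3 imputes from the covariates of the 12-month analysis model. With only the outcome missing, this gives essentially the available-case estimate, and section 5.6 plans no formal comparison of the two time points. This stands too. The gain would come from adding 12-month rhythm, not from imputation as such.

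**The bias needs loss that differs by arm.** The planned measure is the odds ratio, which the second row leaves unchanged. Patients are blind to allocation (section 1.2), and those unlikely to be available for two years are excluded (section 1.6). Both make arm-specific loss less likely, though neither rules it out.

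**Early loss.** Section 1.4.1 already allows approximately 15% for deaths or loss by 12 months, so many patients without a 24-month recording may lack a 12-month one. The SAP does not support saying that most have one.

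**Conclusion.** The point holds as a limited weakness in a secondary analysis. Section 5.6 relies on available cases, plans no sensitivity analysis and leaves unused a strong predictor that the trial records.

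The odds ratio is biased only if loss depends on post-surgery rhythm differently in the two arms. Neither the size nor the direction of the bias can be derived from the SAP: the range of 8.5 to 14.3 points around 11.2 rests on the assumed transition rates and roughly 15% loss.

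It would go too far to say that the 12-month recording removes the bias. It does so only if loss after 12 months is missing at random given that rhythm and the model covariates. It does nothing for loss before 12 months or loss driven by the unseen 24-month rhythm, so a sensitivity analysis is still needed. How deaths are scored at 24 months is a separate matter.

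**What to change.** In section 5.6, replace the restriction to available measurements with the following.

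- **Main analysis:** in the intention-to-treat population, multiply impute missing 24-month rhythm for patients not known to have died, from treatment group, the model covariates and the observed 12-month rhythm (and 6-month rhythm where recorded). Let these relations differ by arm, by imputing within arm or by including treatment interactions. Combine by Rubin's rules.
- **Sensitivity analyses:** keep the available-case analysis, and add one that counts living patients who withdrew or were lost as in AF, following the censored=AF approach of section 5.4.1.

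The cost is a few lines of SAP text and one more imputation model, on data already collected. The downside is some reliance on that model, which the available-case result lets the reader judge.
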